### 13.2 Sample Size/Accrual Rate

At least 2 patients and no more than 21 patients will be accrued onto this trial. Based on our prior experience, we estimate to identify 2-3 eligible patients per month.

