## SCHEMA

- Patients with rectal adenocarcinoma either locally advanced or metastatic rectal adenocarcinoma requiring chemoradiation to the primary lesion are eligible.
- Patients with locally advanced rectal adenocarcinoma (T3 or T4, at risk of having a positive surgical radial margin and/or N+), or patients with metastatic disease requiring chemoradiation.
- Patients will be treated with FOLFOX chemotherapy x 4 doses over 8 weeks (weeks 1-8) followed by short course radiation over 5 days (weeks 9 or 10).
- Subsequently, starting approximately 2 weeks after finishing short course RT, patients will receive FOLFOX chemotherapy x 4 doses (weeks 12 / 13 – 19 / 20). While surgical resection of the primary is not mandatory, those requiring surgery will undergo resection 8-16 weeks later (weeks 27 - 36) and / or further systemic therapy per treating physician's discretion.
- Talimogene laherparepvec will be administered via endoscopy by a qualified physician for a total of 4 doses at the following time points: a) week prior to c1 FOLFOX b) weeks 3, 5 and 7 during FOLFOX
- Dose escalation will be done using a 3 + 3 design over 2 cohorts and a total of 15 patients

Dose level+	TALIMOGENE LAHERPAREPVEC Dose (PFU/ml)	Capecitabine (mg/m  po bid on days of radiation)	Radiation	Comments
1	1x 10  , 1x 10  , 1x 10  , 1x 10 	825	50.4 Gray in 28 fractions	Completed prior to protocol amendment 1/23/21
1 (amended)	1x 10  , 1x 10  , 1x 10  , 1x 10 	N/A	25 Gray in 5 fractions	To be implemented if DLTs noted with DL 2
2	1x 10  , 1x 10  , 1x 10  , 1x 10 	N/A	25 Gray in 5 fractions	

will be treated at MTD.

Dose limiting toxicities (DLTs) will be captured until completion of FOLFOX chemotherapy (weeks 18/9) and will be graded according to the CTCAE ver 5.0.

#Patients with inadequate archival tissue for integrated biomarker analysis

^As part of pre-surgical evaluation or at a corresponding time point in patients not undergoing surgery

+Dose escalation will be done using a 3+3 design for a total of 15 patients that will be treated at MTD

TVEC = talimogene laherparepvec

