- *5-Fluorouracil (5-FU) 400 mg /  $m^2$  IV bolus followed by 5-Fluorouracil (5-FU) 2400 mg /  $m^2$  continuous IV infusion over 46 hours*
- *Leucovorin 400 mg /  $m^2$  IV bolus*
- *Oxaliplatin 85 mg/ $m^2$  IV over 2 hours*

*Weeks 18 / 19:*

- *5-Fluorouracil (5-FU) 400 mg / m^2 IV bolus followed by 5-Fluorouracil (5-FU) 2400 mg / m^2 continuous IV infusion over 46 hours*
- *Leucovorin 400 mg /m^2 IV bolus*
- *Oxaliplatin 85 mg/m^2 IV over 2 hours*

Dose Escalation Schedule				
Dose Level	Dose			Comments
	Talimogene laherparepvec (PFU/ml)	Capecitabine (mg/m  po bid on days of radiation)	Radiation (gray)	
Level 1	1x10  , 1x10  , 1x10  ,1x10 	825	50.4 in 28 fractions	Completed prior to protocol amendment 1/23/21
Level 1 (amended)	1x 10  , 1x 10  , 1x 10  ,1x 10 	N/A	25 Gray in 5 fractions	To be implemented if DLTs noted with DL 2
Level 2 (amended)	1x10  , 1x10  , 1x10  ,1x10 	NA	25 in 5 fractions	

PFU = Plaque forming units; NA = Not applicable

Talimogene laherparepvec will be administered via endoscopy by a qualified physician for a total of 4 doses as before but at the following amended time points: a) week 1 prior to initiation of FOLFOX chemotherapy b) weeks 3, 5 and 7 during FOLFOX chemotherapy

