### 5.3 **Dose Expansion Cohorts:**

A total of 15 patients will be treated at the MTD (including the 6 from dose expansion) to assess safety and feasibility of this dose level. The MTD will be deemed to be recommended phase II dose (RP2D) if  $\geq 80\%$  of the patients are able to receive  $\geq 80\%$  of the planned treatment doses. If  $\geq 1/3$  of all patients at this dose experience DLTs, enrollment will be stopped and the Principal Investigator will discuss with all study investigators and with CTEP whether further addition of patients is needed to re-assess the RP2D. Monitoring of all safety and toxicity data is done by the Principal Investigator and the Corresponding Organization on a real-time basis as data are entered into Medidata Rave using the Web Reporting Module.

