Based on the 3+3 design, the MTD is defined as the highest dose level in which 6 patients have been treated with at most 1 instance of DLT. Thus the target DLT rate is <=16.7%. The study only includes two dose levels, and the following table shows the operating characteristics of the 3+3 design under four different scenarios. For each scenario, the % time selecting a dose as the MTD, the average sample size treated at each dose level, and the probability of stopping the trial early are presented.

Scenario	Doses	1	2
#1	Trued DLT	0.10	0.17
	% MTD	21%	70%
	Average # patients	3.7	3.7
	Prob(early stopping)	0.1	
#2	Trued DLT	0.10	0.25
	% MTD	36%	57%
	Average # patients	3.8	3.9
	Prob(early stopping)	0.08	
#3	Trued DLT	0.40	0.50
	% MTD	26%	5%
	Average # patients	4.3	1.3
	Prob(early stopping)	0.69	
#4	Trued DLT	0.05	0.10
	% MTD	9%	88%
	Average # patients	3.4	3.6
	Prob(early stopping)	0.02	

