Given the novelty and complexity of this study, a review of the data with the sponsor will occur before initiation of new dose levels. A total of 15 patients will be treated at the MTD (including the 6 from dose escalation phase and an addition 9 patients in expansion cohort) to assess safety of this dose level. Up to 15 patients (including the 6 patients treated at the MTD during dose escalation) will be enrolled into the expansion cohort to further confirm the safety of the MTD (as described in the study primary objective) and to assess efficacy and biomarker change (as described in the study secondary & exploratory objectives). With a total sample size of 15 and assuming the true DLT rate is 0.167, then the probability of observing at least one DLT event is 93.5%. If the true DLT rate is 0.30, then the probability of observing at least one DLT event is 99.5%. The MTD will be deemed to be recommended phase II dose (RP2D) if  $\geq 80\%$  of the patients are able to receive  $\geq 80\%$  of the planned treatment doses. If  $\geq 1/3$  of all patients at this dose experience DLTs, enrollment will be stopped and the Principal Investigator will discuss with all study investigators and with CTEP whether further addition of patients is needed to re-assess the RP2D. Monitoring of all safety and toxicity data is done by the Principal Investigator and the Corresponding Organization on a real-time basis as data are entered into Medidata Rave using the Web Reporting Module.

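### The accrual cap of 21 is three short of what the amended plan needs if dose level 2 fails after six patients, unless the completed level 1 patients are meant to count

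*Combined protocol and SAP*

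**What the plan says.** Section 13.2 sets the trial size: "At least 2 patients and no more than 21 patients will be accrued onto this trial". The planned enrollment table below it also totals 21 (2 + 5 + 11 + 3).

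The size of the MTD cohort appears twice. Section 5.3: "A total of 15 patients will be treated at the MTD (including the 6 from dose expansion"). Section 13.1: "A total of 15 patients will be treated at the MTD (including the 6 from dose escalation phase", plus 9 in expansion. The two differ in the word expansion or escalation, but both give 15. Section 13.1 then adds a softer sentence: "Up to 15 patients (including the 6 patients treated at the MTD during dose escalation) will be enrolled into the expansion cohort". It also gives operating figures for 15 patients; at a true DLT rate of 0.167, "then the probability of observing at least one DLT event is 93.5"%, and at 0.30 it is 99.5%.

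Section 13.1 describes the design before the amendment: both levels have 50.4 Gy with capecitabine, and "The study only includes two dose levels". The Schema, Section 2.4 and Section 5.1 now list three rows: level 1 with long-course chemoradiation (completed), Level 1 (amended) with 25 Gy in 5 fractions and no capecitabine, and level 2 with 25 Gy in 5 fractions. The middle row is a fallback: "To be implemented if DLTs noted with DL 2".

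**The concern.** The amendment added a regimen that may have to be taken through six escalation patients and nine expansion patients, after some of the accrual had already been used on a regimen that is now closed. The cap and the design text behind it were not revisited. If the cap is too small in some branch, two firm statements (no more than 21 in all, 15 at the MTD) cannot both be met, and nothing says which gives way. The conflict arises only after level 2 has failed and the dose has been lowered. Without a rule, the size of the MTD cohort would then be chosen after DLTs had been seen.

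**Working it through.** **Inputs**
- Cap: 21 (Section 13.2).
- MTD cohort: 15, made up of 6 from escalation and 9 from expansion (Sections 5.3 and 13.1).
- A level closes at 3 or at 6 patients. It fails with more than 1 DLT, and the MTD needs 6 patients with at most 1 DLT (Sections 5.2 and 13.1).
- Patients used on completed level 1: 3. This is inferred. Section 13.1 starts with a cohort of 3, and Section 2.4 reports the first cohort completed without DLTs. The count itself is not stated.
- Completed level 1 patients do not count toward Level 1 (amended). This is an assumption, taken from the separate row with different radiation and no capecitabine.

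**The plan's own figures**
- Two-level design, largest path: 6 at the level that is not the MTD + 15 at the MTD = 21. The other path gives 3 + 15 = 18. So 21 is the pre-amendment maximum.
- Detection probability is 1 − (1 − p)^15. At p = 0.167 it is 93.5%; at p = 0.30 it is 99.5%. Both match Section 13.1.

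**Amended plan, total patients by branch**

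| Branch | Sum | Total |
|---|---|---|
| Level 2 is the MTD | 3 + 15 | 18 |
| Level 2 fails in its first cohort, Level 1 (amended) is the MTD | 3 + 3 + 15 | 21 |
| Level 2 fails after six, Level 1 (amended) is the MTD | 3 + 6 + 15 | 24 |
| Both amended levels fail after six | 3 + 6 + 6 | 15 |

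Only the third branch breaks the cap. There, 21 − 3 − 6 = 12 patients remain for Level 1 (amended).

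**Effect of 12 instead of 15**
- p = 0.167: 1 − 0.833^12 = 88.8%, against 93.5%.
- p = 0.30: 1 − 0.70^12 = 98.6%, against 99.5%.

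**How likely the third branch is**

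Let p2 be the DLT rate at level 2 and p1 the rate at Level 1 (amended). Level 2 fails after six by 1 of 3 then at least 1 of 3, or by 0 of 3 then at least 2 of 3:

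F6 = P(1 of 3) × P(≥1 of 3) + P(0 of 3) × P(≥2 of 3), at p2.

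Level 1 (amended) is then accepted with probability A = P(≤1 of 6), at p1. The branch has probability F6 × A. The rates are the four scenarios in Section 13.1, with its dose 1 rate applied to Level 1 (amended).

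| Scenario | p1 / p2 | F6 | A | F6 × A |
|---|---|---|---|---|
| 1 | 0.10 / 0.17 | 0.194 | 0.886 | 17% |
| 2 | 0.10 / 0.25 | 0.310 | 0.886 | 27% |
| 3 | 0.40 / 0.50 | 0.391 | 0.233 | 9% |
| 4 | 0.05 / 0.10 | 0.086 | 0.967 | 8% |

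Worked for scenario 1: 0.351 × 0.428 + 0.572 × 0.077 = 0.194, and 0.194 × 0.886 = 0.172. Counting only the 1-of-3 path, the four products are 13%, 22%, 8% and 6%.

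**If the assumptions change**
- Completed level 1 used 6 rather than 3: the first three branches need 21, 24 and 27, and the cap leaves 21 − 6 − 6 = 9 in the last of them.
- The 3 completed patients are pooled with Level 1 (amended): the maximum is 6 + 15 = 21 and the cap holds.

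**The case against.** The strongest reply is pooling. The virus doses at completed level 1 and Level 1 (amended) are the same, the primary objective concerns the MTD of the virus in combination, and the top-up rule in Section 5.2 counts patients already treated at that dose. On that reading 21 is enough. It cannot be ruled out, because no section settles it. It would, however, rest the MTD on two regimens that differ in radiation, capecitabine and injection schedule, so it has to be stated if it is intended.

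The second reply is the softer sentence in Section 13.1, "Up to 15 patients (including the 6 patients treated at the MTD during dose escalation) will be enrolled into the expansion cohort". It weakens the commitment, but the sentence before it and Section 5.3 say that 15 will be treated, and 93.5% and 99.5% are computed for exactly 15.

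The third is that Section 13.1 requires a data review with the sponsor before a new dose level opens. That makes it unlikely that the shortfall goes unnoticed, but it does not raise the cap.

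Some stronger readings are tempting but are not supported:
- A reader might infer that the Schema gives a rival trial total: "Dose escalation will be done using a 3 + 3 design over 2 cohorts and a total of 15 patients". The sentence is split by the dose table, and the Schema footnote shows that 15 is the number treated at the MTD.
- A reader might infer that the RP2D rule fails at 12. It is a proportion with no fixed denominator: 80% means 12 of 15, or 10 of 12, and it still works.
- A reader might infer that the stated minimum of 2 is an error. It remains true once 3 patients have been treated and changes nothing.
- A reader might obtain a higher branch probability by pairing a more toxic level 2 with a well-tolerated level 1. None of the four scenarios in Section 13.1 has such a pair.
- A reader might add patients to replace those who are not evaluable under Section 5.2. That section defines evaluability but gives no replacement procedure, so the totals here are before any replacement.

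**Conclusion.** The conflict holds in one branch. If level 2 fails after six patients and Level 1 (amended) becomes the MTD, the plan needs 24 and the cap allows 21, so 12 rather than 15 patients can be treated at the MTD. The loss in detection probability is modest: 4.7 points at a true rate of 0.167 and 0.9 points at 0.30. Over the protocol's scenarios the branch has a probability of 8% to 27%. No decision rule breaks. The defect is that the stated trial size does not deliver the stated MTD cohort, and no text says which yields.

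This rests on two assumptions that the documents suggest but do not state: 3 patients on completed level 1, and no pooling of those patients with Level 1 (amended). That the cap was carried over from before the amendment is also an inference, from the exact match with 6 + 15 and from the unamended text of Section 13.1. Severity: should-fix.

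**What to change.** In Sections 13.1 and 13.2, state how many patients completed level 1 used and whether they count toward Level 1 (amended). Bring the dose table and design text of Section 13.1 into line with Section 5.1.

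If those patients do not count, choose one of two wordings:
- Restate accrual by branch: 18, 21 or 24, each before any replacement, and change the enrollment table to match.
- Keep 21, and state in Sections 5.3 and 13.1 that the MTD cohort is 12 if level 2 fails after six, with 88.8% and 98.6% printed beside 93.5% and 99.5%.

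If they do count, say so and say that the MTD cohort would then combine two regimens.

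The second wording adds no patients and costs only text, plus a slightly less favourable figure in one branch. The first adds at most three patients, and only in that branch. Either should be settled before Level 1 (amended) opens.

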### PLANNED ENROLLMENT REPORT

Racial Categories	Ethnic Categories				Total
	Not Hispanic or Latino		Hispanic or Latino		
	Female	Male	Female	Male	
American Indian/ Alaska Native	0	0	0	0	0
Asian	1	1	0	0	2
Native Hawaiian or Other Pacific Islander	0	0	0	0	0
Black or African American	2	3	0	0	5
White	3	4	2	2	11
More Than One Race	0	0	2	1	3
Total	6	8	4	3	21

PHS 398 / PHS 2590 (Rev. 08/12 Approved Through 8/31/2015)

OMB No. 0925-0001/0002

### 13.3 Stratification Factors

N/A

### 13.4 Analysis of Secondary Endpoints

Secondary objectives of the study include determining feasibility and NAR.. Feasibility will be reported in all patients who have started therapy as percent of planned dose intensity, NAR will be reported in all patients who undergo resection. NAR will be calculated as detailed in section 2.6 and will be reported using descriptive statistics. pCR will be reported with proportions along with the appropriate confidence intervals and survival by Kaplan-Meier method. Descriptive statistics will be used to report results of other correlative studies discussed above. Tumors will

be characterized into good and poor responders to enable binary comparison. mrTRG is based on similar principles to the pathologic TRG and is based on the degree of tumor replaced by fibrotic stroma on post-treatment pelvic MRI. mrTRG-5 (no fibrosis, only tumor signal visible), mrTRG4 (predominantly tumor signal with minimal fibrotic stroma) will be defined as poor responders whereas mrTRG-1 (no tumor signal) to mrTRG-3 (50% or greater fibrotic stroma) will be defined as good. For the purposes of CRM, a margin greater than or equal to 1 mm between the tumor and the resection margin will be defined as clear (good responder) and the rest as poor responders. Prognosis of good responders including DFS, OS and local recurrence will be compared to that of poor responders. Furthermore, mrTRG will be compared to histological TRG (ypTRG) to validate its accuracy. Two radiologists with extensive experience with rectal MRIs (Drs. [name] & [name]) will read all the scans to minimize inter-observer variability.

**APPENDIX A                    PERFORMANCE STATUS CRITERIA**

ECOG Performance Status Scale		Karnofsky Performance Scale	
Grade	Descriptions	Percent	Description
0	Normal activity. Fully active, able to carry on all pre-disease performance without restriction.	100	Normal, no complaints, no evidence of disease.
		90	Able to carry on normal activity; minor signs or symptoms of disease.
1	Symptoms, but ambulatory. Restricted in physically strenuous activity, but ambulatory and able to carry out work of a light or sedentary nature (e.g., light housework, office work).	80	Normal activity with effort; some signs or symptoms of disease.
		70	Cares for self, unable to carry on normal activity or to do active work.
2	In bed <50% of the time. Ambulatory and capable of all self-care, but unable to carry out any work activities. Up and about more than 50% of waking hours.	60	Requires occasional assistance, but is able to care for most of his/her needs.
		50	Requires considerable assistance and frequent medical care.
3	In bed >50% of the time. Capable of only limited self-care, confined to bed or chair more than 50% of waking hours.	40	Disabled, requires special care and assistance.
		30	Severely disabled, hospitalization indicated. Death not imminent.
4	100% bedridden. Completely disabled. Cannot carry on any self-care. Totally confined to bed or chair.	20	Very sick, hospitalization indicated. Death not imminent.
		10	Moribund, fatal processes progressing rapidly.
5	Dead.	0	Dead.

**APPENDIX D        BIOASSAY TEMPLATES**

*NA*

**APPENDIX E NCI TEMPERATURE EXPOSURE LOG**  
**Talimogene laherparepvec (NSC 785349)**

NCI Protocol Number: \_\_\_\_\_

PMB Order Number: \_\_\_\_\_ (obtain from Shipment Record)

Date Received: \_\_\_\_\_

Maximum exposure time: **90 Seconds**

**Exposure Time**

Start Time = time inner shipping container lid is removed

Stop Time = time --80°C freezer door is closed

Start Time: \_\_\_\_ : \_\_\_\_ : \_\_\_\_ (hour:minute:second - example: 09:50:01)

Stop Time: \_\_\_\_ : \_\_\_\_ : \_\_\_\_ (hour:minute:second - example: 09:50:58)

Confirm time difference from start time to stop time does not exceed 90 seconds:

YES       NO

Comments: \_\_\_\_\_

Name: \_\_\_\_\_ Date: \_\_\_\_\_

Complete one log for each shipping container received.

Retain log with your study records. If exposure time exceeds 90 seconds, quarantine the agent supplies in the -80°C freezer and call PMB immediately at [contact] for guidance.

**APPENDIX F RECEIVING INSTRUCTIONS FOR NCI SUPPLIED TALIMOGENE LAHERPARECVEC (NSC 785349)**

**IMPORTANT: READ THE ENTIRE INSTRUCTIONS BEFORE OPENING THE INNER SHIPPING CONTAINER**

Step 1: Verify all shipment documents are present:

- NCI Shipment Record of Clinical Drug Request
- Temperature Exposure Log

Step 2: Transfer Talimogene laherparepvec vials to  $-80^{\circ}\text{C}$  ( $+\text{- }10^{\circ}\text{C}$ ) freezer  
**You have 90 seconds to verify the contents of the shipping container and place the agent supplies in the  $-80^{\circ}\text{C}$  freezer once the inner container lid is opened and the supply exposed to room temperature**

- Place the shipping container near the  $-80^{\circ}\text{C}$  freezer
- Don gloves per your institutional procedures for handling dry ice
- Open the lid of the inner shipping container
- A second person should record the start time on the temperature exposure log once the lid of inner shipping container is removed
- Open the payload box sleeve and remove the payload box containing the carton(s) of Talimogene laherparepvec
- Open the payload box and remove carton(s) of Talimogene laherparepvec
- Verify agent, strength, quantity and lot number received against NCI Shipment Record of Clinical Drug Request
- Place carton(s) of Talimogene laherparepvec in the  $-80^{\circ}\text{C}$  freezer and close the freezer door
- Record the stop time on the temperature exposure log

Step 3: Complete documentation

- Confirm the time difference from start time to stop time does not exceed 90 seconds
- Complete remainder for temperature exposure log and retain with your study records
- If exposure time exceeds 90 seconds, quarantine the agent supplies in the  $-80^{\circ}\text{C}$  ( $+\text{- }10^{\circ}\text{C}$ ) freezer and call PMB immediately at [contact] for guidance.

1. Siegel, R.L., K.D. Miller, and A. Jemal, *Cancer statistics, 2016*. CA Cancer J Clin, 2016. **66**(1): p. 7-30.
2. Sauer, R., et al., *Preoperative versus postoperative chemoradiotherapy for rectal cancer*. N Engl J Med, 2004. **351**(17): p. 1731-40.
3. Sauer, R., et al., *Preoperative versus postoperative chemoradiotherapy for locally advanced rectal cancer: results of the German CAO/ARO/AIO-94 randomized phase III trial after a median follow-up of 11 years*. J Clin Oncol, 2012. **30**(16): p. 1926-33.
